For participants in the CRYSTALSIGHT group, each participant will have a testing result by CRYSTALSIGHT and by OCT every 4 weeks or less if the positive result triggers a clinical visit. The result is considered correct if it is consistent with the findings of the OCT scan. During the one-year study period, the total number of correct results generated by CRYSTALSIGHT will be counted and the accuracy for these participants will be calculated as number of correct results divided by the total number of clinical visit. For participants in the Amsler Grid group, the accuracy for each participant will also be calculated.

According to literature, the accuracy of Amsler Grid in detecting disease activity was about 80%, we will assume that CRYSTALSIGHT has the same accuracy. For the Singapore population, we will also assume that standard deviation of the accuracy to be 0.12 and setting the maximum allowable difference in accuracy (non-inferiority margin) between the two groups to be 0.09, with one-sided type 1 error of 0.025 and a power of 0.8, a total of 52 participants will be required (26 per group). Considering of 15% attrition rate, a total of 60 participants will be required.

For global study, we assume a higher standard deviation of the accuracy to be 0.21 and a dropout rate of 21%, a total of 220 participants will be required (110 per group).

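### The Singapore sample size of 26 per group gives about 77% power on its own inputs, not 80%, and rests on an unexplained SD close to chance variation alone

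*Protocol*

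**What the plan says.** The last part of the Protocol, Sample size calculation, defines one accuracy per participant: the share of clinic visits over the year at which the home-test result agrees with OCT. Both arms are assumed to have the same mean: "the accuracy of Amsler Grid in detecting disease activity was about 80%, we will assume that CRYSTALSIGHT has the same accuracy".

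Two sizes follow.

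- **Singapore.** The SD is given as "we will also assume that standard deviation of the accuracy to be 0.12". The margin is 0.09. The error rate and target are stated as "with one-sided type 1 error of 0.025 and a power of 0.8". The result is that "a total of 52 participants will be required (26 per group"). Then: "Considering of 15% attrition rate, a total of 60 participants will be required".
- **Global.** "we assume a higher standard deviation of the accuracy to be 0.21", with 21% dropout, giving 220 in total (110 per group). Under Study Design, this total includes the 60 Singapore participants.

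No source is given for either SD or for the difference between them. The Study Schedule Table lists 12 visits, of which 11 follow baseline. The Sample size calculation speaks of visits every 4 weeks, which is about 13 a year. The caption of Figure 5 has a participant leave the study once a device detection is confirmed by OCT.

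**The concern.** A sample size statement should follow from its own inputs, and here the Singapore one does not. The attrition step then adds slightly too few participants.

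The SD also needs support. Accuracy is a proportion over a dozen or so visits per participant, so it varies by chance even if every participant has exactly the same underlying accuracy. An SD near that chance level implies that participants hardly differ. Yet the Protocol says under Recruitment that the device will not work for everyone, and early exit shortens the denominator for some participants.

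At stake is how a Singapore-only result is read. The stated power of 0.8 invites the reader to treat that comparison as adequately powered for non-inferiority. If it is not, a failure to show non-inferiority in Singapore could be mistaken for evidence against the device.

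**Working it through.** **Inputs** (Protocol, Sample size calculation): margin 0.09; true difference 0; one-sided alpha 0.025 (z = 1.96); power 0.8 (z = 0.8416); SD 0.12 for Singapore and 0.21 globally; 1:1 allocation (Study Design).

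**1. The stated sizes.** n per group = 2 × (1.96 + 0.8416)² × SD² / 0.09².

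- Global: 2 × 7.849 × 0.21² / 0.09² = 85.5, so 86 per group or 172 evaluable. 172 / 0.79 = 217.7, so 218; with t, 87 per group and 221. The stated 220 reproduces.
- Singapore: 2 × 7.849 × 0.12² / 0.09² = 27.9, so 28 per group or 56 evaluable (29 per group with t). The stated 26 does not reproduce.
- Other conventions do not explain 26: one-sided 0.05 gives 22 per group, and a single binary outcome per participant gives 311 per group.

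**2. Power of the stated size at SD 0.12.** Power = Φ(0.09 / (SD × √(2/n)) − 1.96).

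- n = 26: 0.09 / (0.12 × 0.2774) = 2.704; Φ(0.744) = 77.2% (75.6% with t).

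**3. Attrition.** 52 × 1.15 = 59.8, which gives the stated 60. To have 52 left after losing 15%, one divides: 52 / 0.85 = 61.2, so 62. With 60 enrolled, 60 × 0.85 = 51 remain.

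- 51 remaining (25.5 per group): Φ(2.678 − 1.96) = 76.4%.
- All 60 retained (30 per group): Φ(2.905 − 1.96) = 82.8% (81.5% with t).

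**4. How SD 0.12 compares with chance.** If visits are independent with a common accuracy of 80%, the SD of a participant's proportion over v visits is √(0.8 × 0.2 / v).

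| Visits scored | Chance SD | Excess SD left within 0.12 |
|---|---|---|
| 11 (follow-up visits) | 0.1206 | none |
| 12 (all listed visits) | 0.1155 | √(0.0144 − 0.01333) = 0.033 |
| 13 (every 4 weeks) | 0.1109 | √(0.0144 − 0.01231) = 0.046 |

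The 12-visit chance SD, put into the formula in step 1, gives 2 × 7.849 × 0.01333 / 0.0081 = 25.8, so exactly 26. This may be where 26 came from, but the Protocol does not say so.

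**5. Sensitivity at 26 per group.** Each line depends on an SD that the Protocol does not assume for Singapore.

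- An assumed between-participant SD b is added to 11-visit chance variation: SD² = 0.16/11 + b² × (1 − 1/11). With b = 0.05 the SD is 0.130 and power 71%; with b = 0.10 the SD is 0.154 and power 56%.
- If the total SD were 0.15: Φ(2.163 − 1.96) = 58%.
- If only 6 visits were scored on average, with no differences between participants: SD √(0.16/6) = 0.163 and power 51%.
- If Singapore shared the global SD of 0.21: Φ(1.545 − 1.96) = 34%.

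**The case against.** The strongest reply is that the gap which the Protocol's own inputs prove is small, 77% against 80%, and that larger gaps need inputs from outside the Protocol. That is right. It does not remove the error, but it limits its size. Four stronger readings should be set aside.

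- **That 0.12 is no larger than chance.** A reader might infer this from the 11 follow-up visits. It holds only at that count: at 12 or 13 visits a little room remains. The chance SD is also a model. If a participant's accuracy differs between visits with active and inactive disease, the variance within a person can be somewhat below the binomial value.
- **That 0.12 and 0.21 contradict each other.** They do not. The Protocol labels the global SD as higher, and a three-country sample may be more variable than one site. With equal site means, both hold if the other sites have SD √((220 × 0.21² − 60 × 0.12²) / 160) = 0.235. What stands is that no reason is given for the difference.
- **That Singapore falls short even with perfect follow-up.** It does not: 30 per group at SD 0.12 gives about 83%. The shortfall at SD 0.12 assumes that the planned attrition occurs.
- **That Singapore's real power is 34%.** That applies only if Singapore shares an SD which the Protocol assumes for the global study alone.

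Two further points are fair. The Protocol foresees missed home tests rather than missed clinic visits, and it describes early exit only after a correct device detection, so the number of visits lost is unknown. Nor does it call Singapore a separate confirmatory test; Study Design describes one trial of 220, and that size reproduces.

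**Conclusion.** The point holds as an error in the stated Singapore size and power. On the Protocol's own inputs, 28 per group are needed rather than 26. Power is about 77% with 26 per group and about 76% with the 51 participants left after 15% attrition. This conclusion needs no outside assumption beyond the usual normal approximation, and the t-test makes it slightly worse.

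The remark on the SD is a second, softer conclusion. It rests on independent visits with a common 80% accuracy and on 11 to 13 scored visits. Under those assumptions 0.12 is near the floor, so any real difference between participants, or a shorter visit record, would lower power further. By how much cannot be settled from the Protocol. The documents support an unexplained and optimistic SD, not an impossible one. The global size of 220 is unaffected.

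**What to change.** In the Sample size calculation:

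- Replace the Singapore power of 0.8 with about 77% at SD 0.12 for 26 per group after attrition.
- Correct the attrition step: either state that 60 enrolled less 15% leaves 51 (about 76% power), or divide by 0.85 when inflating.
- Give the basis for SD 0.12, including the expected number of scored visits and the variation between participants, and say why the global SD is 0.21.
- Add a sensitivity range for larger SDs, marked as conditional: for example about 58% at an assumed 0.15, and 34% if Singapore shared the global 0.21.
- State that the 220-participant comparison is the powered test and that Singapore alone does not reach 80% on the stated inputs.

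This costs only wording and a less favourable Singapore figure; no extra patients are needed. If the sponsor prefers to keep the 0.8 claim at SD 0.12, 56 / 0.85 = 65.9, so 66 Singapore participants would have to be enrolled.

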This is a randomised, open-label, non-inferiority clinical trial comparing two parallel arms: a standard care arm using Amsler Grid home monitoring (PRN), and an intervention arm using the CRYSTALSIGHT gaze-tracking system (PRN+). A total of 220 (Singapore – 60, United Kingdom – 80, United States – 80) participants will be randomised in a 1:1 ratio. Participants in the intervention arm will self-administer biweekly CRYSTALSIGHT tests at home, while those in the control arm will use the Amsler Grid. Both arms will attend monthly clinic visits for standard evaluations, including VA, BCVA, and OCT. Alerts generated by the CRYSTALSIGHT system based on deviation thresholds will trigger early clinic recall for confirmatory imaging and potential re-treatment.

[figure not shown]

Figure 4 Details of the home-use clinical trial study design. The trial objective: show that PRN+ is non-inferior to standard of care PRN with better VA/VF outcomes

Development of CRYSTALSIGHT cutoff scores should have been conducted in the cohort-1 1 study [NCT: NCT06518512] (Analysis). This Phase 2 should be the application of validated cut-off scores. The second aim will be to compare the accuracy of CRYSTALSIGHT and Amsler, and sensitivity and specificity check.

In addition to identifying CRYSTALSIGHT visual risk prediction cut-off scores, detection yields, and diagnostic Performance indicators will also be evaluated. Progression to CNV was

OCCUTRACK

determined by the investigator, based on standardised OCT confirmation. At the clinical trial site, these events were confirmed by gradings conducted by masked, certified independent personnel who did not know the treatment assignment. Events from both arms are graded using a standardised protocol.

[figure not shown]

Figure 5 In Cohort 2, home-based score deviation detected, study coordinator will schedule hospital checkup immediately. If CRYSTALSIGHT correctly detects wet AMD recurrence confirmed by OCT, subject exits the study.

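### Singapore sample size: the stated inputs need 28 evaluable per group (29 by t), not 26, and 60 randomised with 15% attrition gives about 75–76% power, not 80%

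*Protocol*

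**What the plan says.** The section "Sample size calculation" of the protocol defines accuracy for each participant as the share of clinic visits at which the home test agrees with OCT. It then compares the mean of that share between the two arms. From the literature it takes it that "the accuracy of Amsler Grid in detecting disease activity was about 80" per cent, and it assumes the same for CRYSTALSIGHT.

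For Singapore it adds "standard deviation of the accuracy to be 0.12", "setting the maximum allowable difference in accuracy (non-inferiority margin) between the two groups to be 0.09" and the error rates "with one-sided type 1 error of 0.025 and a power of 0.8". It concludes that "a total of 52 participants will be required (26 per group"), and then: "Considering of 15% attrition rate, a total of 60 participants will be required".

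For the global study it changes only the SD (0.21) and the dropout rate (21%) and states "a total of 220 participants will be required (110 per group"). The section "Study Design" gives 1:1 randomisation and divides the 220 by country as "Singapore – 60, United Kingdom – 80, United States – 80", so the Singapore figure of 60 is carried into the recruitment plan.

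**The concern.** The Singapore paragraph gives every input that a non-inferiority comparison of two means needs, so its result can be checked directly. The result does not follow. The required number is understated, and the allowance for attrition does not preserve even that understated number. Both errors act in the same direction.

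What is at stake is the protocol's claim of 80% power for the 60 Singapore participants. Someone judging a Singapore result that failed to meet the margin would think that part of the trial had a better chance of success than it had. The size and power of the 220-participant comparison are not in question.

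**Working it through.** **Inputs** (all from "Sample size calculation", except the allocation, from "Study Design"):

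| Input | Singapore | Global |
|---|---|---|
| True difference in accuracy | 0 | 0 (carried over) |
| SD of accuracy | 0.12 | 0.21 |
| Margin | 0.09 | 0.09 (carried over) |
| One-sided type 1 error | 0.025 | 0.025 (carried over) |
| Power | 0.80 | 0.80 (carried over) |
| Allocation | 1:1 | 1:1 |
| Attrition | 15% | 21% |
| Stated evaluable N | 52 (26 per group) | not stated |
| Stated randomised N | 60 | 220 |

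The protocol does not restate the margin, error rate and power for the global study. Carrying them over is an assumption.

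**Step 1: which formula supports the protocol's figures.** For non-inferiority of means with no true difference, n per group = 2 × (z₀.₉₇₅ + z₀.₈₀)² × (SD/margin)².

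- Global: 2 × (1.960 + 0.842)² × (0.21/0.09)² = 85.5, so 86 per group and 172 in total. 172/0.79 = 217.7, so 218, close to the stated 220. Conversely, 220 × 0.79 = 173.8 evaluable (86.9 per group) gives power 80.6% (normal) or 80.2% (t). The formula supports 220, though not to the last participant.

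**Step 2: the same formula for Singapore.**

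- 2 × (1.960 + 0.842)² × (0.12/0.09)² = 27.9, so 28 per group and 56 in total.
- By the noncentral t distribution, power is 78.7% at 28 per group and 80.1% at 29, so 29 per group and 58 in total.
- The protocol states 26 per group and 52 in total.

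**Step 3: can another reading give 26?** One-sided type 1 error 0.05 gives 22 per group; one-sided 0.0125 gives 34; power 0.90 gives 38; a binary endpoint at 80% in both arms gives 311. None gives 26. With the other inputs fixed, the normal formula gives 26 if the SD is 0.12 × √(26/27.9) = 0.116, or if the margin is 0.09 × √(27.9/26) = 0.0932. Neither value is stated.

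**Step 4: attrition.**

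- 60 × 0.85 = 51, below the stated 52.
- Keeping 52 needs 52/0.85 = 61.2, so 62 randomised.
- The stated 60 matches 52 × 1.15 = 59.8, which multiplies by one plus the rate where division by one minus the rate is needed. The global figure fits the division: 172 × 1.21 would be only 208.

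**Step 5: power delivered.** Normal approximation: Φ(0.09 / [0.12 × √(1/n₁ + 1/n₂)] − 1.960). The t column uses the noncentral t distribution.

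| Evaluable in Singapore | Normal | t |
|---|---|---|
| 26 + 26 (as stated) | 77.2% | 75.6% |
| 26 + 25 (60 less 15%) | 76.3% | 74.7% |
| 28 + 28 | 80.1% | 78.7% |
| 29 + 29 | 81.5% | 80.1% |
| 30 + 30 (no attrition) | 82.8% | 81.5% |

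Sixty randomised therefore reach 80% only if attrition is at most 1 − 56/60 = 6.7% (normal) or 1 − 58/60 = 3.3% (t), against the assumed 15%.

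**The case against.** The best counter-argument is rounding. The SD and margin are printed to two decimals, and an SD of 0.1158 or a margin of 0.0932 would print as the stated values and give 26 by the normal formula. Over the full rounding ranges (SD 0.115 to 0.125, margin 0.085 to 0.095) the formula runs from 23.0 to 33.9 per group. This is a possible origin of the 26, but it does not rescue the text. The protocol does not say that its inputs were rounded, and a reader cannot recover the result. By t, changing one input alone would need an SD of 0.1136 or a margin of 0.0951, both outside the rounding range; both inputs would have to move together. Nor does rounding repair the attrition step: with SD 0.1158 and 26 + 25 evaluable, the normal formula gives Φ(0.09/[0.1158 × 0.2801] − 1.960) = Φ(0.815), about 79%. What stands is that, if unrounded inputs were used, the true shortfall would be smaller than the one computed here.

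It can also be said that the attrition error is a single participant against the stated 52 and costs under one point of power. That is right, and it is the secondary part of the point.

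Finally, the protocol describes one trial of 220 and sets no separate test or success rule for Singapore, so a failed Singapore result is a reader's scenario. This limits the consequence. It does not make the sentence correct: the protocol chose to give Singapore its own SD, attrition rate and power.

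**Conclusion.** The point holds. On the stated inputs, Singapore needs 56 evaluable participants (normal) or 58 (t), not 52, and the 60 to be randomised deliver about 75–76% power after the stated attrition, a shortfall of roughly 4 to 5 percentage points. This rests on taking the printed inputs at face value, comparing per-participant accuracy as a mean between equal arms, and losing 15% overall so that 26 and 25 remain.

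The practical impact is modest and confined to the Singapore statement. The 220-participant comparison is unaffected, provided the margin, type 1 error and power given for Singapore also apply globally.

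**What to change.** Keep 60 for Singapore and replace the two sentences with something like:

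> Under these assumptions, 56 to 58 evaluable participants (28 to 29 per group) would be needed for 80% power. Sixty will be randomised in Singapore; about 51 are expected to remain after 15% attrition, giving power of about 75% to 76%.

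If the 26 came from unrounded inputs, print those inputs and still correct the attrition step (52/0.85, so 62 randomised).

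The cost is two sentences and a less favourable stated power for Singapore. No participants are added, and the global number and the division by country stay as they are. If the sponsor prefers to restore 80% in Singapore, 28/0.85 = 32.9 gives 33 per group (66 randomised) by the normal formula, and 29/0.85 = 34.1 gives 35 per group (70 randomised) by t. That is 6 to 10 more than planned.
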